### **7.6.2 Physical Examination**

The number (%) of patients with screening physical examination abnormalities will be tabulated for the safety population and all physical examination data will be displayed in a listing by treatment group.

### **7.6.3 Vital Signs**

Vital signs from each visit and the change from the baseline to each post-baseline visit will be summarized using descriptive statistics for the safety population. No formal inferential tests of significance will be performed. All vital signs data will be listed by treatment group and patient.

### **7.6.4 Laboratory investigations**

Laboratory investigations of hematology, biochemistry and urine analysis tests performed for the safety population at screening (Visit I) will be repeated at TOC to ensure study subject safety and will be summarized accordingly.

### **7.6.5 Prior or Concomitant Medication**

Incidence of prior or concomitant medications will be summarized by treatment group, and by the number and percentage of patients taking each medication, and will be classified using World Health Organization Drug Dictionary (WHO-DD) Anatomical Therapeutic Chemical (ATC) classes and preferred terms.

### **7.6.6 Medical History**

Medical history will be captured at baseline and will be tabulated and listed by treatment group.

## **8. STUDY CONDUCT**

This section details general conventions to be used for the statistical analyses. Departures from these general conventions may be given in the specific detailed sections of this analysis plan.

### **8.1 Subject Accountability and Disposition**

The subject accountability and disposition information will be summarized for each treatment group. The subject accountability may include and not limited to number of subjects screened, enrolled, randomized, treated, discontinued before study completion and study completed. The subject disposition may include number of subjects in each population, study completion status and primary reason for discontinuation from the study. These summary reports will be generated using all randomized population and grouped by randomized treatment with total as a separate column.

### **8.2 Demographics and Baseline Characteristics**

Demographic characteristics including age, gender, race, ethnicity, height, weight and body mass index (BMI) will be summarized by treatment groups for the safety, mITT & Per-Protocol population.

The comparability of treatment groups with regard to patient demographic characteristics will be evaluated using descriptive statistics. No inferential analyses are planned.

Gender, race, ethnicity will be summarized as frequency distribution by treatment group.

Patient's age in years at the time of consent will be derived as follows:

$$\text{Age} = [(\text{Date of Consent} - \text{Date of Birth}) + 1] / 365.25 \text{ and truncated to completed years.}$$

[figure not shown]
Baseline patient characteristics will include medical history and will be coded and tabulated by body system and preferred term using MedDRA, version 18.1 or higher.

Baseline and post-baseline patient characteristics will include physical examination, vital signs, and lab data, prior and concomitant medications.

Investigational product administration will be summarized for each patient and include total duration of exposure. Descriptive statistics including the mean, SD, minimum, and maximum will be provided by treatment group for safety population.

### **8.3 Study diary Completion**

Study drug diary completion will begin on Study Day 1 and end on last study visit. Diary completion includes recording of temperature if a subject feels feverish; date/time of study drug

each dose; date, time and consistency of stool; as well as enteric infection symptoms (abdominal pain or cramps, excessive gas/flatulence, nausea, vomiting, fecal urgency, blood and/or mucus in the stool, tenesmus)

#### **8.4 Enteric Infection and Other Symptoms**

The number of subjects with enteric infection symptoms (abdominal pain or cramps, excessive gas/flatulence, nausea, vomiting, fecal urgency, blood and/or mucus in the stool, tenesmus) from the study diary and other symptoms (Fever, Moderate or severe dehydration) will be summarized and percentage will be calculated on mITT and per-protocol populations on all visits by treatment group.

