9.5 Analysis of Safety Parameters

All adverse events (AEs) and treatment-emergent AEs (TEAEs) reported during the study will be summarized/reviewed in order to assess safety. Safety will be evaluated by incidence of TEAEs including incidence of selected TEAEs of special interest, incidence of SAEs; TEAEs by relationship to study drug and intensity; and TEAEs leading to discontinuation. Observed results and change from baseline in clinical laboratory tests, vital signs, and physical examinations will be tabulated by treatment group.

MedDRA (using the latest available version) will be used to classify all AEs with respect to SOC and preferred term. All safety summaries will be performed on the safety analysis set by treatment group without inferential statistics.

Total extent of exposure to study drug will be measured by total number of tablets taken and duration of exposure calculated as date of last dose minus date of first dose plus 1. Study drug compliance (%) will be calculated as number of tablets taken divided by number of tablets expected to take multiplied by 100. Subjects are considered to have good compliance if the compliance (%) is within the range of ~75% to ~125%, corresponding to 7 to 11 doses.

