#### 4.2 Safety Endpoints

The safety endpoints are:

1. Number and proportion of subjects reporting adverse events
2. Changes in clinical laboratory tests, vital signs, and physical examinations from baseline
3. Prior or Concomitant Medication
4. Medical History
5. Enteric symptoms

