### 4.5 Modified intent-to-treat (mITT)

The modified intent-to-treat (mITT) is a subset of the safety analysis set consisting of all randomized subjects who meet all inclusion and none of the exclusion criteria, received at least one dose of study drug and provided efficacy and safety data after one dose of study drug. The mITT set is the basis for testing superiority of each active arm compared to the placebo with respect to primary efficacy endpoint i.e. clinical cure rate.

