## **7.6 Safety Analysis**

All Safety analysis will be summarized based on safety population and all safety summaries will be provided by treatment group.

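### SAP 8.4 summarises a named safety endpoint on mITT and PP rather than the safety population, and SAP 7.6.1 and 7.6.2 omit two safety tables that the protocol calls for

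*SAP*

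**What the plan says.** **Symptom summary.** SAP 4.2 lists "5. Enteric symptoms" among the safety endpoints, on a separate line from adverse events. SAP 7.6 gives the general rule: "All Safety analysis will be summarized based on safety population and all safety summaries will be provided by treatment group". Protocol 9.5 gives the same rule for the safety analysis set. SAP 8.4, which covers the diary enteric symptoms, fever and dehydration at all visits, says instead that "other symptoms (Fever, Moderate or severe dehydration) will be summarized and percentage will be calculated on mITT and per-protocol populations". It does not name the safety population.

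**TEAEs of special interest.** Protocol 7.4 lists nine: fever, moderate or severe dehydration, hematochezia, abdominal pain or cramps, nausea, vomiting, fecal urgency, excessive gas, and tenesmus. Protocol 9.5 requires their incidence: "Safety will be evaluated by incidence of TEAEs including incidence of selected TEAEs of special interest". SAP 7.6.1 plans tables of TEAEs by system organ class and preferred term, by severity and by relationship, with safety-population denominators. It does not mention special interest.

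**Physical examination.** SAP 4.2 and protocol 7.4 make change from baseline an endpoint, and protocol 9.5 says that it will be tabulated. SAP 7.6.2 specifies one table: "The number (%) of patients with screening physical examination abnormalities will be tabulated for the safety population". All other examination data go to a listing.

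**The concern.** The SAP gives two different bases for one safety endpoint. A programmer who follows 8.4 literally will leave some dosed subjects out of the summary of enteric symptoms, fever and dehydration. The mITT set is restricted to "all randomized subjects who meet all inclusion and none of the exclusion criteria", with the further condition of post-dose efficacy and safety data. The safety set requires only one dose.

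The other two gaps concern content, not population. Without a special-interest table, the events that the protocol singled out are scattered across preferred terms. Without a post-dose examination table, the planned tabulation says nothing about what happened after treatment. At stake is the descriptive safety comparison of generic, reference and placebo. The bioequivalence and superiority tests are not affected.

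**Working it through.** **1. Is the basis in 8.4 contradictory or a deliberate convention?**

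- SAP 4.2: enteric symptoms are a safety endpoint.
- SAP 7.6 and protocol 9.5: safety summaries use the safety population.
- SAP 8.4: mITT and PP.
- SAP 8.5, the next section: percentages for formed and unformed stool frequencies, also diary data, use the safety population.

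So 8.4 does not follow a general rule for diary data, and no reason for the departure is given.

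**2. Who is in the safety set but not in mITT?** By the SAP definitions (headed 4.4 and 4.5 in the body, 5.2 and 5.3 in the contents list):

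- dosed subjects who breached any inclusion or exclusion criterion;
- dosed subjects who did not provide both efficacy and safety data after dosing.

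The first group can have complete diaries. In the second, a subject with post-dose safety data but no efficacy data may have symptoms to count. A subject with no post-dose data at all would add only to the denominator.

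**3. How many?** Inputs: 618 randomised and a planning loss from randomised to mITT of 15% (SAP 7.2). The target mITT size is not legible, so the sample size cannot be independently reproduced. As a consistency check only, 525 / 0.85 = 617.6, which rounds up to 618.

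- mITT at the planning figure: 618 × 0.85 = 525.3.
- Not in mITT: 618 × 0.15 = 92.7. At 1:1:1 this is 206 × 0.15 = 30.9 per arm.
- Let u be the share of randomised subjects never dosed (not given in the documents, so an assumption). Dosed subjects outside mITT = 618(1 − u) − 525.3.

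| u (assumed) | Dosed | Dosed, not in mITT | Share of safety set |
|---|---|---|---|
| 0% | 618.0 | 92.7 | 15.0% |
| 5% | 587.1 | 61.8 | 10.5% |
| 10% | 556.2 | 30.9 | 5.6% |
| 15% | 525.3 | 0 | 0% |

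**4. Do the TEAE tables make up for 8.4?** In part. Fever, dehydration or an enteric symptom reported as a TEAE is counted for every dosed subject in SAP 7.6.1. But under protocol 7.5 an event present before dosing is a TEAE only if it then becomes more frequent or more severe. Inclusion criterion 3 requires at least one enteric symptom at entry, so every eligible subject starts with one. A symptom that persists unchanged is not a TEAE and would be summarised only under 8.4.

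**5. Can special-interest incidence be read off the preferred-term tables?** Not reliably. A category such as abdominal pain or cramps may span several preferred terms. Adding rows would count a subject with two such terms twice, whereas protocol 7.4 counts subjects.

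**6. Physical examination.** Examinations are done at Visits 1 and 3 (protocol 7.7). SAP 7.6.3 gives vital signs, part of the same endpoint line, a change to each post-baseline visit. SAP 7.6.2 gives the examination a table at screening only. SAP 8.2 names the examination among post-baseline characteristics but defines no table.

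**The case against.** The best defence is that most of the safety information survives. SAP 7.6.1 counts all TEAEs on the safety population, so these events are not lost when reported as adverse events. Fever and enteric symptoms are also components of clinical cure, so an mITT or PP table has a legitimate efficacy use. All examination data are listed. The table shells are in a separate document (SAP Appendix I) and may already contain a special-interest or post-baseline table. These points stand, and they limit the finding. They do not remove the contradiction between 8.4 and SAP 4.2 and 7.6, nor supply the two summaries missing from the SAP text.

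A reader might infer more, and the documents do not support it:

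- *That the subjects at highest risk are the ones dropped.* Exclusion criterion 3 (fever, blood in stool, dehydration) overlaps with the events in 8.4, but it is one of 13 criteria and nothing shows that it is the one breached. Subjects with no post-dose data would, if added, lower the percentages.
- *That users of prohibited medication and early discontinuations vanish.* These are grounds for leaving PP. Neither is an mITT exclusion in itself, and the SAP expressly keeps early discontinuations for other reasons in mITT.
- *That the examination table loses subjects.* It already uses the safety population. Its defect is a missing time point.

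**Conclusion.** The point holds as an internal contradiction and two omissions. SAP 8.4 uses mITT and PP for an endpoint that SAP 4.2, SAP 7.6 and protocol 9.5 together place on the safety population. SAP 7.6.1 names no special-interest TEAE summary, and SAP 7.6.2 has no post-dose examination table.

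The number of dosed subjects missing from the 8.4 summary is unknown. The range of 0 to about 93 of 618 rests on the 15% loss, which is a planning assumption and not an enforced cap, and on an unstated share never dosed. PP can only be smaller than or equal to mITT if it is drawn from it, but its definition is largely illegible here and no figure is offered. The effect on the reported percentages cannot be sized, in amount or direction, because the documents give no symptom rates for those left out.

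This should be corrected before database lock. It is a matter of descriptive safety reporting and does not alter the primary conclusions.

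**What to change.** - **SAP 8.4:** name the safety population as the basis for the safety summary of enteric symptoms, fever and dehydration. Keep the mITT and PP versions as supportive.
- **SAP 7.6.1:** add a by-treatment table, on the safety population, of the number and percentage of subjects with each of the nine TEAEs of special interest in protocol 7.4. State which preferred terms make up each category.
- **SAP 7.6.2:** add a Visit 1 to Visit 3 shift table (normal or abnormal, by body system) on the safety population.
- Check the separate table shells and bring them into line with the revised text.

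The cost is SAP wording and two or three extra tables from data already collected. Nothing changes for sites or subjects.

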7.4 Safety Parameters

Safety parameters will include the following:

1. Treatment emergent adverse events (TEAEs)
2. Subjects with the following TEAEs of special interest
 - a. Fever
 - b. Moderate or severe dehydration
 - c. Hematochezia (blood in stool)
 - d. Abdominal pain or cramps
 - e. Nausea
 - f. Vomiting
 - g. Fecal urgency
 - h. Excessive gas/flatulence
 - i. Tenesmus
3. Changes in clinical laboratory tests, vital signs, and physical examinations from baseline

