### 4.4 Safety Population

All randomized subjects who receive at least one dose of study drug will form the Safety Analysis Set. The Safety Analysis Set will be used for all analyses of safety, tolerability, and background characteristics.

[figure not shown]

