#### **8.5 Stool Data and Results**

Number of formed and unformed bowel episodes will be listed per subject by treatment group and time on randomized population.

The number of subjects will be distributed to the corresponding frequency of formed and unformed bowel episodes by treatment group. The percentage will be calculated based on safety population.

Stool Culture Results of E.coli (ETEC & EAEC), Other Microorganism (example: Campylobacter, Salmonella, Shigella), Stool microscopy for ova and parasites will be summarized on the values of present or absent by treatment in Day 1 and TOC visits on mITT & Per-Protocol Population.

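### The SAP's declared safety endpoint of enteric symptoms is summarized on the mITT and PP sets, not the safety population, without separating new from persisting symptoms, and the visible SAP has no table of the protocol's special-interest TEAEs

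*SAP*

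**What the plan says.** Protocol 7.4 includes among the safety parameters "Subjects with the following TEAEs of special interest" and names nine: fever, moderate or severe dehydration, hematochezia, abdominal pain or cramps, nausea, vomiting, fecal urgency, excessive gas, and tenesmus. Protocol 9.5 adds: "Safety will be evaluated by incidence of TEAEs including incidence of selected TEAEs of special interest". It places every safety summary on the safety analysis set.

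The SAP handles this in several places:

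- SAP 4.2 does not name the special-interest TEAEs. Its fifth safety endpoint is "Enteric symptoms".
- SAP 7.6 sets the general rule: "All Safety analysis will be summarized based on safety population". The Safety Population section (4.4 in the body) agrees: "The Safety Analysis Set will be used for all analyses of safety, tolerability, and background characteristics".
- SAP 7.6.1 plans AE and TEAE tables by system organ class, preferred term, severity and relationship, plus tables for SAEs and for events leading to withdrawal. No special-interest table is visible.
- SAP 8.4 takes the diary symptoms plus fever and dehydration, and says the counts "will be summarized and percentage will be calculated on mITT and per-protocol populations on all visits by treatment group".
- SAP 8.5, the next section, says of stool-episode frequencies: "The percentage will be calculated based on safety population".

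The mITT set is a subset of the safety set. It is limited to subjects "who meet all inclusion and none of the exclusion criteria" who also gave efficacy and safety data after a dose.

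**The concern.** There are two separate problems. First, the SAP calls enteric symptoms a safety endpoint and then summarizes them on sets that its own safety rule does not name. Dosed subjects who failed an entry criterion are in the safety set but are left out of both 8.4 displays.

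Second, 8.4 counts whoever has the symptom at each visit. Subjects enter the trial ill, so a symptom at a later visit may be unresolved diarrheal illness or something that began on treatment. Both documents define treatment-emergent as new or worsened (protocol 7.5; SAP Definitions), but 8.4 applies no such rule. The protocol's own answer was the special-interest TEAE summary, and the visible SAP does not carry it over.

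At stake is how readable the by-arm safety comparison is for the events that the protocol singled out. The primary inference is not involved.

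**Working it through.** **Item match.** Protocol 7.4 has nine items and SAP 8.4 has nine. Eight match. The ninth is hematochezia in the protocol, but in the diary it is pooled with mucus in the stool (protocol 6.2; SAP 8.4). So 8.4 covers nearly the right symptoms. What it lacks is the analysis set and the treatment-emergent rule.

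**Which items can be present at entry.** Inclusion criterion 3 (protocol 4.1) lists abdominal pain or cramps, nausea, vomiting, urgency, gas and tenesmus, which are six of the nine. Exclusion criterion 3 (protocol 4.2) rules out the other three: fever, hematochezia and dehydration. The new-versus-persisting problem therefore concerns six items. Every mITT subject must have at least one of the six, so their average Visit 1 prevalence in that set is at least 1/6, about 17%.

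**Size of the set difference.** Inputs: 618 randomized and about 15% lost between randomization and mITT (SAP 3.5), with equal allocation (the 1:1:1 heading in SAP 7.2).

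- The planned size is consistent with this loss: 175 / (1 − 0.15) = 205.9, so 206 per arm, and 3 × 206 = 618.
- Outside mITT: 618 × 0.15 = 92.7, about 93. Per arm: 206 × 0.15 = 30.9, about 31.
- These figures include subjects never dosed, who are not in the safety set either. The split is not given, so the number dosed but outside mITT lies between 0 and about 93.

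If k dosed subjects per arm are added to 175 in mITT, the arm's percentage moves by [k / (175 + k)] × (rate in the added subjects − rate in mITT). For a 10-point difference in rates, with k assumed:

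| k per arm | Weight | Shift |
|---|---|---|
| 0 | 0 | 0 points |
| 10 | 10/185 = 0.054 | 0.5 points |
| 31 | 31/206 = 0.150 | 1.5 points |

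The last row is a ceiling. It assumes that every lost subject was dosed and has symptom data. These are also shifts within one arm; similar shifts in all arms largely cancel in the comparison.

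**What by-visit counts reveal about new symptoms.** Let b be prevalence at Visit 1 and c prevalence later in the same subjects. The share absent at Visit 1 and present later lies between max(0, c − b) and min(c, 1 − b). With assumed values:

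| b | c | New symptoms, range |
|---|---|---|
| 50% | 15% | 0% to 15% |
| 10% | 15% | 5% to 15% |
| 90% | 15% | 0% to 10% |

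The documents give no symptom rates, so these only illustrate the point: two marginal counts bound the new symptoms but do not identify them. Worsening of a symptom already present is outside these bounds altogether.

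**The case against.** The case for leaving this alone has several parts.

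- **AE reporting covers the events.** Protocol 7.5 asks for an AE form for each sign or symptom when there is no diagnosis, and SAP 7.6.1 tabulates TEAEs by preferred term and arm on the safety population. This stands for events that sites report as AEs. It does not give subject incidence for an event spread over several preferred terms, because a subject can appear in more than one row.
- **Absence is not proven.** The shells are in a separate document (SAP Appendix I). The SAP introduction treats the protocol's methods as still specified, and protocol 9.5 speaks of selected events. All true. The point is therefore about the visible SAP, and a citation would settle that part.
- **mITT and PP are natural sets for symptom course.** Enteric symptoms are part of the cure definition, and SAP 4.2 is a loose list that also includes medical history. SAP 8 also allows departures from its general conventions. This is fair as a reason to keep the two displays. But 8.4 gives no reason for leaving out the safety population, and 8.5 shows that it can be used for diary data.

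A reader might infer that none of the nine events is displayed, or that diary symptoms are seen only in 8.4. Neither is supported. Section 8.4 names eight of the nine, protocol 9.1 puts all eCRF items into listings and appropriate summary tables, and SAP 7.5.1 tabulates reasons for clinical failure. A reader might also infer that someone who stops early because of vomiting drops out of view. The PP rules are not fully visible, such a subject can still be in mITT, and an AE leading to withdrawal has its own table and listing.

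**Conclusion.** The point holds as a conflict within the SAP and an incomplete carry-over from the protocol. A declared safety endpoint is summarized on sets that the SAP's own safety rule does not name. Its by-visit counts cannot separate new from persisting symptoms for six of the nine events, and the special-interest summary promised in the protocol is not in the visible SAP.

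The practical size is modest and partly unknown. The figure of about 93 should not be read as 93 safety subjects lost from the display. It is a planning ceiling that includes undosed subjects, and dosed subjects excluded for giving no post-dose data would add little symptom information. The main gain would be dosed subjects who failed entry criteria, whose number is not given. The direction of any distortion against placebo cannot be stated. The analysis is descriptive, and the equivalence and superiority tests do not depend on it. Even so, it should be corrected, because the protocol specified this safety display and supplying it is cheap. Confidence is medium because the shells were not seen.

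**What to change.** In SAP 7.6.1, add one descriptive by-arm table, on the safety population, of the protocol 7.4 TEAEs of special interest. Use the protocol 7.5 definition (new after the first dose, or worse than before it), list the preferred terms mapped to each event, and give hematochezia its own line. If the shells already contain this table, cite it there instead.

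In SAP 8.4, add the safety population and show symptoms by Visit 1 status (absent then present later, versus persisting) wherever that status is recorded symptom by symptom. Keep the mITT and PP displays, labelled as symptom course.

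The cost is one or two extra descriptive tables from data already collected. Two limits remain. The visible diary fields carry no symptom severity, so worsening can be judged only from AE records. If blood and mucus share one diary field, the hematochezia line must also come from AE records.
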